Composition: Each 1 ml contains: hyaluronic acid 20 mg, Sorbitol 40 mg, phosphate buffered solution 1ml. Synolis VA contains a 2 ml siringe of viscoelastic solution.

Contraindications.

Synolis VA should not be used in:

- Patients known to be hypersensitive to hyaluronic acid or sorbitol.
- Pregnant lactating patients
- Minors
- Skin disease or infection at the level of the application site.

CLINICAL EVALUATION

The knee injury and Osteoarthritis Outcome Score (KOOS) is a new, well-designed, and simple self-administered instrument developed to assess short, and long-term symptoms and function in patients with knee injuries and osteoarthritis. It has good evidence of reliability, validity, and responsiveness in different populations with different pathologies, injury duration, ages, and activity levels. The KOOS scale has been shown to be very effective in Young and active patients; it is intended to be used in short and long-time intervals; to assess week-to-week changes induced by treatment (medication, surgery, physical therapy). All items were scored from 0 to 4, and each of the five scores was calculated as the sum of the included items; scores are then converted to a scale of 0-100, where zero represented extreme knee problems and 100 represented no knee injury, this can be represented as a percentage.

The INTERNATIONAL KNEE DOCUMENTATION COMMITTEE IKDC, is a patient-oriented score to qualify symptoms and functions related to the activity of daily living; evaluates knee injuries and categorizes them into subjective variables, symptoms, ranges of motion and ligamentous exploration, which is subcategorized into normal, almost normal, abnormal and severely abnormal, the objective of this scale is to provide the physician with information on patient satisfaction and their knee. Points on the *Subjective Knee Assessment Form* are calculated by adding the points for the individual items, and then transforming the points on a scale from 0 to 100. The transformed points are interpreted as a measure of the ability to function, with higher points representing higher levels of functioning and lower levels of symptoms. One hundred points are interpreted to mean that there is no limitation in activities of daily living or sports activities, and the absence of symptoms.

Justification and Statement of the Problem

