Currently there is a major influence to promote sport in the population, however, despite its great benefits, the development of early osteoarthritis secondary to micro-trauma due to overuse must be taken into consideration. In fact, the presence of early osteoarthritis following a prolonged or intense period of physical activity, or in those who practice impact sports regularly, is well described. Athletes who have initial stages of osteoarthritis require a treatment that improves their clinical symptoms and improves functional functions for as long as possible. Another objective of treatment is for their daily sports activities; sports activities; intraarticular HA injections are more effective in young patients, especially in the long term, while the results are less promising in athletes with advanced osteoarthritis. Reducing the viscoelasticity of synovial fluid, the transmission of mechanical force to the cartilage increases susceptibility to mechanical damage. Therefore the restoration of normal joint homeostasis is the reason for the administration of hyaluronic acid in the joints, in addition to seeking a physiological healing process and, if possible, complete; secondly, to shorten the recovery time, especially in athletes who are not going to limit their activity. The currently evidence that exists regarding the efficacy and safety of viscosupplementation in athletes is limited, hence the present investigation arises from the understanding that there are no protocols that demonstrate the benefits of knee joint infiltration using hyaluronic acid plus sorbitol in athlete patients, so in order to determine the safety and efficacy of this treatment, the following research question is proposed:

RESEARCH QUESTION

Is there a clinical and functional difference in the short and medium term in patients with knee pain due to overuse associated with sports treated by infiltration with hyaluronic acid with sorbitol?

Hypothesis

Athletes with sports-related overuse knee pain have Good clinical and functional results in the short and medium term through joint infiltration of hyaluronic acid with sorbitol.

Null Hypothesis

Athletes with knee pain due to sports-related overuse do not have Good clinical and functional results in the short and medium term through joint infiltration of hyaluronic acid with sorbitol.

Objectives

General Objective

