To evaluate safety and efficacy of hyaluronic acid with sorbitol in athletes with overuse knee pain by comparing functional outcomes at short, medium and long term after treatment.

Specific Objectives

- To assess the safety and efficacy of hyaluronic acid with sorbitol in patients with sports-associated knee pain.
- To compare the clinical and functional results of patients with sport-associated knee pain after before and after treatment.

METHODS

Study Design

This research will be a cohort study, prospective and unidirectional direction.

Selection Criteria

- Patients with knee pain for more than 3 months
- Patients between 30 and 55 years old
- Patients without a history of previous knee joint surgery.
- Patients without chronic-degenerative diseases such as diabetes, hypertension, rheumatoid arthritis or other autoimmune diseases.
- Patients who perform impact social sports at least 3 times a week for more than 1 hour in the last 3 months prior to treatment.
- Patients without a history of allergies to non-steroidal anti-inflammatory drugs.
- Patients with no history of infection in or around the knee.

EXCLUSION CRITERIA

- Patients who cannot be categorized as social athletes.
- Patients with an associated sports injury that limits their sports practice.
- Patients who have a treatment associated with knee pain independent of that established in the study protocol.

ELIMITATION CRITERIA

- Patients who suffer from an injury or illness during the study that may limit their sports activity or who require an analgesic or anti-inflammatory treatment other than that established in the protocol.
- Patients who personally want to leave the study.
- Patients who did not have complete follow-up during the study.
- Patients who present an allergic or infectious reaction related to hyaluronic acid or prolotherapy or sepsis and antisepsis methods for infiltration.
- Patient with an allergic reaction to non-steroidal anti-inflammatory drugs.

VARIABLES

Variable	Operational Definition	Dimension	Variable type	Instrument	Indicator
Age	Time of life of any person	Without categories	Quantitative Discrete	Interview	Years
Gender	Biological and physiological characteristics that differentiate a man from a woman	Female Male	Qualitative Nominal	Interview	Gender
Body Mass Index	Score calculated by weight and height of a person.	Normal Overweight Obesity	Quantitative Discrete	Measuring tape Weighing machine	Weight in kg / Height in square meters

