Affected Knee	Anatomic Knee side	Left	Qualitative	Physical Exploration	Left

		Right	Nominal		Right
Athlete	Person who practice any type of sport	Social Amateur Professional	Qualitative Nominal	Interview	Have a sports activity for more than 3 months, 3 times a week over 60 minutes per session
Score KOOS	Scores that evaluate functional and osteoarthritis around the knee	Symptoms Joint Stiffness Pain Regular activities Sports activities Quality of life	Quantitative Discrete	Interview Physical Exam	Percentage 0-100%
Score IKDC	International Knee Documentation Committee	Symptoms Regular Activities Sports Activities	Quantitative Discrete	Interview Physical exam	Percentage 0-100%
Visco supplementation	Intraarticular joint injection of high weight molecular hyaluronic acid with sorbitol	Mono dose Multi dose	Qualitative Nominal	Hyaluronic acid 2ml plus sorbitol 2 dose per knee	Yes = Knee joint infiltration No= Did not apply
Training sports technique	Coaching for adequate techniques of certain sports	Manual technique Instrumented	Qualitative Nominal	Personalized coaching techniques	Achievement survey

	activities			Or Information brochure	
--	------------	--	--	----------------------------	--

Research Universe

General Population who does sports activities and have knee overuse syndrome between June of 2022 and October 2022.

Sample Size

It will be a non-probability sampling where will be chosen participants who meet selection criteria over the enrolling time which will be for 5 months. The lower limit will be 60 participants and the higher limit will be 120 participants.

Sample size formula: $n(\text{sample})$, z (confidence level), p (probability to occur the studied event), q (probability to didn't occur the studied event) and e (maximum accepted estimated error)

$$Z^2 * p*q$$

$$n = \frac{Z^2 * p*q}{e^2}$$

Study Design

Research enrolling and diffusion will be initiated after authorization of the ethics and investigation committee. All participants with knee pain related to sports will be accepted for a physical evaluation. All participants will be interviewed about physical activities, sports, injuries, and knee pain. Once they have been categorized as athletes with knee overuse pain syndrome and have met the selection criteria, then will be invited to the research. For this, the participants must be agreed and sign the informed consent Appendix 1 and 2.

Before treatment Group

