To participants who initiate the study research will be applied the KOOS and IKDC scores, the results will be recorder in the collection data sheet. Appendix 2. Participants will be explored by physical exam focus on knee pathology, and also an echography knee scan

looking for non-overuse pain injuries. Coaching for sports activities will be explained for each patient in order to improve its own training techniques adding stretching exercises for previous and after training.

After treatment Group

After KOOS and IKDC scores were recorded two doses of Hyaluronic Acid plus sorbitol will be applied. Technique: On the examination table, the patient will lie down at supine position and the area of the knees to be infiltrated will be discovered. Asepsis of the knee region will be performed using an iodine and alcohol solution, the remaining synovial fluid in the joint will be extracted with a 10cc syringe then 4 milliliters of 80 mg of hyaluronic acid plus 160 mg of sorbitol will be applied (Synolis VA Aptissen S. A.) at the sub quadriceps level with a 22G x 32mm sterile needle. At the end of the infiltration, the needle will be removed, and the injection site will be covered with a small sticky-band, which can be thrown away after 20 minutes. It will be recommended to not make any kind of sports activity following the next 72 hours and apply ice therapy 3 times per day for over 20 minutes. Scores recorded data will be made at 15 days, then at 3 and 6 months.

Once the enrolling phase of the trial is concluded, statistical analysis will be made with Excel Office software for Windows, IBM SPSS and Prism.

Statistical analysis

Recorded data of the functional scores will be evaluated before and after treatment, also at 15 days, 3 and 6 months after hyaluronic acid supplementation.

Data analysis will be made by means standard deviation for numeric variables, also t-test for parametric and Wilcoxon Mann Whitney for non-parametric variables, a standard error of 95% is allowed. Differences in time will be calculated and group compared by Anova test. Variable correlation and association measures with relative risk and attributable risk with Fisher's test will be made with a confidence interval of 95%.

Ethical Implications

This research project will be developed after approval of the ethics and research Institutional committee.

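### The before-and-after comparison tests for a non-zero mean change, so it cannot establish the hypothesised 'Good' results or credit them to the injection

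*Combined protocol and SAP*

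**What the plan says.** The Null Hypothesis section states that athletes with sports-related overuse knee pain "do not have Good clinical and functional results in the short and medium term through joint infiltration of hyaluronic acid with sorbitol". The Hypothesis is its positive counterpart.

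The design has one treated group. The Methods section says: "This research will be a cohort study, prospective and unidirectional direction". The 'before treatment' and 'after treatment' groups are the same people, scored at baseline, 15 days, 3 months and 6 months. The second specific objective is "To compare the clinical and functional results of patients with sport-associated knee pain after before and after treatment".

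The analysis matches that objective: "Recorded data of the functional scores will be evaluated before and after treatment". The tests are described as "also t-test for parametric and Wilcoxon Mann Whitney for non-parametric variables, a standard error of 95% is allowed", with ANOVA for differences over time. Relative risk and Fisher's test are also named, but no event is defined for them.

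No section gives a KOOS or IKDC cut-off, a minimum change, a responder definition or a reference rate for 'Good'. The Clinical Evaluation section describes both 0-100 scales and the IKDC grades from normal to severely abnormal, but ties none of them to the hypothesis.

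**The concern.** The claim and the test are about different things. The hypothesis speaks of the quality of the result and of its cause, the infiltration. The analysis can show only that mean scores moved from baseline. With no level set for 'Good', rejecting zero change leaves open whether the change is large enough to deserve that word.

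A positive mean change could also arise without any product effect:

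- The Diagnosis section describes inflammation that comes and goes, with long spells of few symptoms in between.
- The selection criteria require more than 3 months of knee pain, so people enter while symptomatic.
- Every participant gets coaching on technique and stretching exercises, and is advised to use ice and to avoid sport for 72 hours after the injection. The section on treatment of knee overuse syndrome counts better technique, stretching and ice among effective first-line measures.
- The elimination criteria remove people who need other analgesics or lack complete follow-up.

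At stake is the wording of the conclusion. Followed as written, the plan could support a statement of good results through joint infiltration from a detectable mean change alone.

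**Working it through.** **The mismatch needs no arithmetic.** The stated null is 'results are not Good'. The null that a before-and-after t-test or rank test addresses is, in substance, 'no change from baseline'. Rejecting the second does not reject the first unless 'Good' means any change above zero, and the protocol does not say that.

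**The plan's own figure.** The Sample Size section says: "The lower limit will be 60 participants and the higher limit will be 120 participants". Its formula, n = Z²pq/e², comes without values for Z, p or e and without a defined event, so 60 and 120 cannot be reproduced. Solving backwards with Z = 1.96 and p = 0.5 gives e = 12.65% at n = 60 and 8.95% at n = 120. The formula concerns a proportion, so it sets no size of score change that could stand in for 'Good'.

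**How small a significant mean change could be (illustration).**

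- From the documents: n = 60 and n = 120; 0-100 scales; a 95% confidence level.
- Assumed: a paired test (the plan does not say), two-sided 5%, everyone analysed, and an SD of change of 10 to 20 points, with 25 added to show sensitivity.
- Formula: smallest significant mean change = t(0.975, n−1) × SD / √n.
- Example at SD 15: 2.001 × 15 / √60 = 3.87, and 1.980 × 15 / √120 = 2.71.

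| SD of change | n = 60 | n = 120 |
|---|---|---|
| 10 | 2.58 | 1.81 |
| 15 | 3.87 | 2.71 |
| 20 | 5.17 | 3.62 |
| 25 | 6.46 | 4.52 |

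**Comparison with one answer step.** On KOOS scoring the protocol says: "All items were scored from 0 to 4". Items are summed within each subscale and rescaled to 0-100. One step on one item is therefore 100 / (4 × items), with item counts from Appendix 2:

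- Sport, 5 items: 100/20 = 5.00
- Quality of life, 4 items: 100/16 = 6.25
- Symptoms, 7 items: 100/28 = 3.57
- Pain, 9 items: 100/36 = 2.78
- Daily living, 17 items: 100/68 = 1.47

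For IKDC, the item maxima in Appendix 1 (current function only for question 10) add to 87, so one raw point is 100/87 = 1.15.

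On KOOS sport, the smallest significant mean change is below one step only if SD < 5√n / t. That gives 5 × √60 / 2.001 = 19.4 at n = 60 and 5 × √120 / 1.980 = 27.7 at n = 120. If 48 of 60 remained (an assumed 20% loss), the limit would be 17.2. If the test were run unpaired, the limits would apply to the SD of the score itself and would be 13.8 (n = 60) and 19.7 (n = 120).

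The comparison does not carry over to the longer subscales. At n = 60 with SD 15 the 3.87 points needed exceed one step on symptoms, pain and daily living. At n = 120 with SD 20 the 3.62 points needed do too. IKDC steps are finer than all but those of daily living among these three, and finer than those as well: 1.15 against 1.47.

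**The case against.** The best defence is that the analysis fits the rest of the protocol. The research question asks whether there is a clinical and functional difference, and the specific objective is a before-and-after comparison. Nowhere does the analysis section say that a significant test will be taken as proof of 'Good' results. This stands, and it places the mismatch in the wording of the hypothesis and of any conclusion drawn from it. It does not remove the mismatch, because the stated null is the only one the protocol gives.

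A reader might go further and infer that any non-zero gain, or any gain smaller than one KOOS sport step, would reject the null. The documents do not support that. A change must be statistically detectable. The SD of change is not given, and at n = 60 with SD 20 the gain needed is 5.17 points, above the 5-point step. Sport and quality of life are also the two subscales with the largest steps. Finally, an answer step is the resolution of one person's score. It does not measure whether a group mean is clinically trivial, so the figures show what could be significant and not that such a change would be unimportant.

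It is also fair to say that setting a threshold for 'Good' would not control for natural fluctuation or for the accompanying advice. That stands, and it is why the attribution to the injection needs separate rewording.

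**Conclusion.** The concern holds as a mismatch between test and claim. The planned comparison addresses a mean change of zero, while the hypothesis asserts 'Good' results brought about by the infiltration. A significant result would establish neither the quality nor the cause. This conclusion rests on the protocol text alone.

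The size is illustrative and conditional. With a paired two-sided 5% test and an SD of change of 10 to 20 points, mean changes of 2.6 to 5.2 points (n = 60) or 1.8 to 3.6 points (n = 120) would be enough for significance. The documents support neither the statement that a sub-step gain would always be significant nor the statement that the treatment has no effect.

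**What to change.** **Preferred.** Reword the hypothesis, null and conclusion along the lines of: *KOOS and IKDC scores change from baseline at 15 days, 3 months and 6 months after treatment*. Drop 'Good' and the phrase crediting the infiltration. Report the mean change at each visit with its 95% confidence interval. This brings the hypothesis into line with the research question and the specific objective.

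**If 'Good' is kept.** Name the score, the visit and the minimum change, with its source. Report the percentage of participants reaching it with a 95% confidence interval, and judge 'Good' against that value rather than against zero. Enrolment was planned for June to October 2022 and the document is dated 01/12/2023, so scores may already have been seen. If so, label the threshold post hoc. The wording on cause should be softened under this option too.

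**Cost.** A few sentences in the hypothesis and analysis sections, and no new data. The downside is that the claim becomes more modest under the first option and harder to meet under the second.

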Drug treatments commonly include the use of pain relievers such as aspirin or acetaminophen, and nonsteroidal anti-inflammatory drugs (NSAIDs); The use of NSAIDs is controversial due to the absence of histological inflammatory response in knee overuse syndrome. There is also concern that NSAIDs may interfere with the normal healing response of muscles and tendons.

INFILTRATIONS

- Platelet Rich Plasma (PRP) injections have been studied for the treatment of tendinopathy and osteoarthritis, obtaining Good medium-term results in the treatment of recalcitrant patellar tendinopathy by applying multiple injections. The use of PRP has been qualified by the Clinical Practice Guidelines of the American Academy of Orthopedic Surgeons (AAOS) for the treatment of knee osteoarthritis, however their decision was that it's use cannot be recommended for or against treatment of knee osteoarthritis.

INFILTRATION WITH HIALURONIC ACID

Visco-supplementation with hyaluronic acid is one of the most recommended treatments for the non-surgical management of osteoarthritis, it can be recommended as first-line therapy, or when corticosteroids and non-steroidal anti-inflammatory drugs are inefficient, contraindicated or poorly tolerated; viscosupplementation is a safe procedure, without any systemic or local side effects, excluding possible injection pain and a feeling of heaviness for a few hours or days after treatment. Hyaluronic acid is one of the most used methods to preserve the cartilage and intra-articular structures of the knee. It protects the chondrocytes and lubricates the joint to stabilize the cartilage and the synovial membrane, benefits have also been described in its analgesic and intra-articular structures of the knee. It protects the chondrocytes and lubricates the joint to stabilize the cartilage and the synovial membrane, benefits have also been described in its analgesic and anti-inflammatory effects. Viscosupplementation significantly reduces knee pain during the first months, after which the effect is maintained for another 12 to 18 months. During this time joint function can improve and therefore patients can quickly return to sports activities.

Physiotherapy

A fundamental part of the overuse syndrome treatment is to know that mistakes in techniques of training could be avoided by guidelines of different type of exercises. Physical therapy should focus on stretching inflexible muscles and tendons (for

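### Does the mismatch between a short, medium and long term objective and a short and medium term hypothesis leave the 6-month scores without a role?

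*Combined protocol and SAP*

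**What the plan says.** The General Objective speaks of "comparing functional outcomes at short, medium and long term after treatment", which is three horizons. The Research Question asks "Is there a clinical and functional difference in the short and medium term", which is two. The Hypothesis says that athletes "have Good clinical and functional results in the short and medium term through joint infiltration of hyaluronic acid with sorbitol", and the Null Hypothesis says that they "do not have Good clinical and functional results in the short and medium term". Both again name two horizons. The second specific objective names none and only compares before with after treatment.

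The visits are given the same way throughout. The After treatment Group section states: "Scores recorded data will be made at 15 days, then at 3 and 6 months". The Abstract has the same schedule, and the Statistical analysis section lists the pre-treatment scores and the same three follow-up times. For the analysis itself it names a t-test, a Wilcoxon Mann Whitney test and an ANOVA for differences over time. It does not say which visit is short, medium or long term, names no principal visit, and does not define what makes a result good.

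**The concern.** With three terms in the objective, two in the hypothesis and three visits tied to none of them, the status of the 6-month scores looks open. If 6 months is long term, those scores serve the objective but lie outside the hypothesis. If 6 months is medium term, they test the hypothesis, but no visit is left for the objective's long term.

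The worry is about timing. Suppose patients improve at 15 days and 3 months and then lose the benefit by 6 months. An author who has seen the scores could call the 6-month result long term and report the hypothesis as supported, or call it medium term and report it as not supported. If that freedom were real and consequential, the terms would have to be fixed in the plan before the data are read.

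**Working it through.** **Step 1: which labellings fit.** The plan has no figure of its own to reproduce here, so the first check is a comparison of the texts. Assign the visits (15 days, 3 months, 6 months) to short (S), medium (M) and long (L) without going backwards in time. There are 10 such assignments. Requiring at least one visit each for short and medium leaves three:

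| 15 days | 3 months | 6 months | Visits in the hypothesis | Long term in the objective |
|---|---|---|---|---|
| S | M | L | 15 days, 3 months | served by 6 months |
| S | M | M | all three | no visit |
| S | S | M | all three | no visit |

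The first row is the plain reading: three terms, three visits, in order. Under it the texts do not contradict each other. The objective is simply wider than the hypothesis, and the 6-month scores are analysed as part of the objective.

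**Step 2: what changes in the results.** Under every row the scores at 15 days, 3 months and 6 months are collected and enter the analysis, because the Statistical analysis section names the visits and not the terms. The tables, tests and intervals are the same. Only the label in the concluding sentence differs.

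**Step 3: could the label reverse the conclusion?** That needs a rule for when the hypothesis counts as supported, and the plan has none. Assumptions for illustration:

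- one score, two-sided 5% tests, improvement as the direction;
- mean change of 0.5 SD at 15 days and 3 months, and zero at 6 months;
- correlation 0.5 between changes;
- n = 60, the lower of the two limits under Sample Size ("The lower limit will be 60 participants and the higher limit will be 120 participants").

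The chance that the hypothesis is supported, by simulation:

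| Assumed rule | 6 months outside the hypothesis | 6 months inside |
|---|---|---|
| Every covered visit significant | 94% | 2.5% |
| At least one significant visit per term (15 days short; 3 and 6 months medium) | 94% | 94% |
| Mean change over the covered visits | 99% | 87% |
| Repeated-measures ANOVA over the covered times, with baseline | 98% | over 99% |

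The third row can be checked by hand. With two visits the mean change is 0.5 and its SD is √((1 + 0.5)/2) = 0.866, so the standardised effect is 0.5/0.866 × √60 = 4.47. With three visits the mean is (0.5 + 0.5 + 0)/3 = 0.333 and the SD is √((1 + 2 × 0.5)/3) = 0.816, which gives 0.333/0.816 × √60 = 3.16. Set against a critical value of about 2.0, these give 99% and 87%.

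At n = 120 the first rule gives over 99% against 2.5%. The other three give at least 99% either way.

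The 2.5% in the first row is only the one-sided error rate of a single test at a visit where the assumed effect is exactly zero. If the effect at 6 months is 0.2 SD, the first rule gives 94% against 33% (n = 60) and over 99% against 58% (n = 120). If it holds at 0.5 SD, it gives 94% against 92% and over 99% for both.

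**Step 4: side remarks.** The background section on hyaluronic acid infiltration says of viscosupplementation in general "after which the effect is maintained for another 12 to 18 months". That neither defines long term for this study nor sets its follow-up. The Study Design text also places the analysis early: "Once the enrolling phase of the trial is concluded, statistical analysis will be made with Excel Office software for Windows". Enrolment lasts 5 months, so no 6-month score can exist when it closes. The Abstract waits for all data, and doing so satisfies both sentences.

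**The case for a change.** The best case for a change is that no labelling serves all three terms of the objective and also brings every planned visit under the hypothesis, that no other section settles the matter, and that one sentence would. Under a rule requiring significance at every covered visit the gap is very large, and whether the effect fades is part of what the 6-month visit is there to show.

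The textual part stands: the terms differ and are undefined. The large contrast does not stand as a property of this plan. It needs both a fading effect and a decision rule that the documents do not contain, and under the other rules tried it shrinks or vanishes. The ANOVA is the only over-time test the plan names. As an omnibus test it does not say when an effect occurred, so it does not settle the label, but neither does it reward choosing one.

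Defining the terms would also not remove the freedom it is aimed at. A result can still be called good or not good at will while that word has no threshold and no principal score or visit is named. That is a separate and larger matter.

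Lastly, the study population is dated June to October 2022 and the document 01/12/2023. If enrolment ran to schedule, some or all 6-month scores may already exist, and labels added now could not count as set in advance.

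**Conclusion.** The inconsistency is genuine, but it is one of wording, and no change to the plan follows. All three follow-up visits are collected and analysed whatever they are called. A sensible analyst reports each of them and states the conclusion by visit (15 days, 3 months, 6 months), so a reader can see a fading effect directly and does not depend on the words medium or long. Aligning the terms would add no visit, score or analysis and would alter no estimate.

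No probability for the effect on the conclusion can be taken from the documents. The range shown, from no difference to 94% against 2.5% at n = 60, rests on assumed effect sizes, an assumed correlation and an assumed rule for support. The judgement rests on one condition that the plan already sets: that the 6-month scores are analysed and reported together with the earlier ones.
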